Date: December 20, 2016

Principal Investigator: [name]

Application Number: IRB00081746 (IND # 128487 – IND Sponsor: [name])

Study Title: Safety, Efficacy, and Feasibility of High-dose Cholecalciferol in Pediatric Patients with Cystic Fibrosis

Principal Investigator: [name]

Application Number: IRB00081746 (IND # 128487 – IND Sponsor: [name])

Document: Protocol to accompany reported study results

NCT02613884

Date: December 20, 2016

Principal Investigator: [name]

Application Number: IRB00081746 (IND # 128487 – IND Sponsor: [name])

JHM IRB - eForm A – Protocol

Safety, Efficacy, and Feasibility of High-dose Cholecalciferol in Pediatric Patients with Cystic Fibrosis

1. Abstract

Children and adults with Cystic Fibrosis (CF) are at risk of developing a vitamin D deficiency or insufficiency, defined as a 25-hydroxyvitamin D (25OHD) serum blood level <30 ng/mL. Greater than 85% of people with CF have pancreatic insufficiency, which contributes to poor absorption of fat soluble vitamins and dietary fats. A 25OHD level greater than 30 ng/mL has been shown to provide improvements to markers of inflammation in adults with CF and is known to improve bone mineral density and prevent bone fractures in all populations, including CF. This study will assess the safety of a one-time high dose of cholecalciferol or vitamin D3 along with efficacy and feasibility of providing this therapy.

Children between the ages of 3 years and 18 years (inclusive), with a 25OHD level <30 ng/mL will be provided with a vitamin D3 supplement of 250,000 international units (IU) observed in our CF clinic. We hypothesize that this one-time, oral, high dose of vitamin D3 will safely and effectively raise the 25OHD level to above 30 ng/mL.

Safety will be monitored using a tiered safety protocol. Within the first tier, a serum calcium level and a serum phosphorus level will be measured at 1 week and 3 months following the dosage. This timing is appropriate as cholecalciferol has a half-life of 2-3 weeks and these timed levels would be at or near the middle of the 25-OHD range. A second tier safety evaluation will only be done if serum calcium levels or serum phosphorus levels are elevated. For this second tier, the participant will have a parathyroid hormone level measured (PTH) as well as a spot urine calcium to creatinine ratio.

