Research has displayed that the human body's response to vitamin D3 is biphasic, meaning it responds rapidly to low vitamin D3 doses and responds much slower to a larger vitamin D3 dose. Heaney et al. found that the low doses of vitamin D3 had a half-life of 20-30 days, but a high dose, such as 100,000 IU vitamin D3 had a half-life of 50 days (10). The authors hypothesized that perhaps at this higher dosage the vitamin D3 is being stored in fat and other body tissues and then slowly released; whereas the daily low doses of vitamin D3 provide an immediate increase or response that can sometimes be reflected in the blood sample.

In children and adults without malabsorption disorders, the current recommended range of daily vitamin D intake ranges from 400 IU per day for children as recommended by the American Academy of Pediatrics (11). Whereas the Institute of Medicine or IOM recommends a range of 600 IU to 4000 IU per day based on the age of the child. The IOM committee did increase its "upper level intake". That dose is 4,000 IU/day for adults, 3,000 IU/day for kids aged 4-8, 2,500 IU/day for kids aged 1-3, 1,500 IU/day for infants aged 6-12 months, and 1,000 IU/day for infants aged 0-6 months. The Endocrine Society for Patients at risk for vitamin D deficiency recommend a daily requirement of 400 IU-1000 IU for children depending on age and their upper level intake is 2000-4000 IU per day depending on age as well (12, 13). However, these recommendations are not for children with absorption disorders such as Cystic Fibrosis.

According to the National Institutes of Health, 25-OHD levels which are consistently greater than 200 ng/mL are "potentially toxic" (13). The IOM committee found no conclusive evidence that increased vitamin D levels confer increased health benefits, challenging the concept that "more is better". However, this was meant to be applied to healthy populations. A review of literature conducted in 2013 displayed that intoxication from vitamin D supplementation was rare in the pediatric setting. This same review also found that hypervitaminosis was "usually asymptomatic" and errors in formulation of the vitamin, manufacturing or prescription of the vitamin resulted in intoxication (13).

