Regardless of serum calcium level or other labs collected, if a participant does become ill after taking the high dose of vitamin D3 (e.g., muscle weakness, confusion, vomiting, anorexia, polyuria and polydipsia, etc.) they will be asked to call the CF office number, [contact]. During this communication, it will be decided if any type of treatment will be needed to remedy the complaint (see section on treatment of hypervitaminosis D from hypercalcemia). If their serum calcium level was within normal limits for age, but they have symptoms of those found with hypercalcemia, it will be noted in our study findings but not classified as an adverse event.

At 12 weeks (± 30 days) from the initial study visit, participants will be required to have another 25OHD level measured via venipuncture as a part of standard of care. In addition, as a part of the

Date: December 20, 2016

Principal Investigator: [name]

Application Number: IRB00081746 (IND # 128487 – IND Sponsor: [name])

first tier of safety measures, a serum calcium and serum phosphorus level will be measured again. If either of these levels is elevated, a PTH level will be measured as soon as possible within approximately 14 days (\pm 3 days) of this serum calcium lab draw. If serum calcium level is above ULN a spot urine calcium to creatinine ratio will be ordered. At 26 weeks (\pm 30 days) and 52 weeks (\pm 30 days) the participants will have 25OHD levels measured again. No additional one-time high dosage of vitamin D3 will be prescribed or provided during the study period for any reason to any of the participants. No additional measures of safety, in the forms of serum calcium labs, serum phosphorus, or PTH will be measured.

Any participant with an elevated serum calcium level of anything above normal limits for age will be instructed to limit calcium containing foods in their diet, stop supplements with additional vitamin D and/or calcium. Since these participants will be called regarding their elevated serum calcium level to query about symptoms of hypercalcemia, we will be able to instruct them on this.

If at any time after the study intervention has started and the participant has a 25OHD level less than 30 ng/mL, they will be placed on the current standard CF Foundation step-wise guidelines for treatment appropriate for their low vitamin D level.

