*** 2nd tier safety assessment using PTH will only be performed in the event serum calcium levels or serum phosphorus levels are elevated greater than the upper limit of normal for age. A spot urine calcium to creatinine ratio will be done. Repeat calcium and phosphorus will be provided every 2 weeks until normalized.

5. Inclusion/Exclusion Criteria:

1. Exclusion Criteria:

- a. Any history of kidney disease, kidney stones, or on dialysis
 - b. Any history of hypercalcemia above upper limits of normal for age within the last six months (see appendix B for normal calcium levels).
 - c. Elevated serum phosphorus level at screening
 - d. Elevated spot urine calcium to creatinine ratio at screening
 - e. Abnormal serum creatinine level 2 times the upper limit of normal for age within the last 6 months
 - f. History of unresolved, abnormal liver function (ALT or AST > 4 times upper limit of normal (ULN)) or any history of portal hypertension.
 - g. Pregnant or breast feeding adolescent females; upon enrollment, will test urine sample for pregnancy in females 8 years and older
 - h. Any history of parathyroid disorders
 - i. Inability to swallow pills by mouth
- ### 2. Inclusion Criteria:
- a. Children with Cystic Fibrosis \geq 36 months of age
 - b. Serum/blood 25OHD level < 30 ng/mL
 - c. Ability to provide valid informed consent to be a part of the study
 - d. Negative urine pregnancy test upon enrollment

6. Drugs/ Substances/ Devices

This trial is being conducted under Investigational New Drug (IND) application # 128487 – IND Sponsor: [name]; all relevant FDA regulations will be followed.

Cholecalciferol (Vitamin D3) capsules from Biotechpharmaceutical will be used. Each capsule has 50,000 International Units of Vitamin D3. Each participant will be provided with 250,000 IU Vitamin D3 (5 capsules) regardless of age, sex or 25OHD level.

The dosage of 250,000 IU Vitamin D3 has been shown to be safe and effective in raising the 25OHD level in adult patients with CF and dosages higher than this have been shown to be safe and effective at raising 25OHD levels in pediatric patients as young as 36 months old with dosages of 100,000 IU Vitamin D3 in addition to pediatric patients 12 years old receiving 400,000 IU Vitamin D3 as a one-time dosage without any adverse events, including hypercalcemia.

The safety of high dose of Vitamin D3 has not been evaluated in pediatric CF patients in the U.S.

7. Off-Treatment and Off-Study Criteria

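### The half-life used to justify the safety draws conflicts with the Background's high-dose figure, and on either figure the end-of-study 25OHD proportion does not measure the efficacy of the single dose

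*Combined protocol and SAP*

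**What the plan says.** Section 1 (Abstract) sets the first-tier safety samples: "a serum calcium level and a serum phosphorus level will be measured at 1 week and 3 months following the dosage". It gives one pharmacokinetic reason, which refers to the range of 25OHD: "This timing is appropriate as cholecalciferol has a half-life of 2-3 weeks and these timed levels would be at or near the middle". Neither the range nor its middle is defined.

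Section 3 (Background) reports that "low doses of vitamin D3 had a half-life of 20-30 days" but that "a high dose, such as 100,000 IU vitamin D3 had a half-life of 50 days". It adds that the body reacts much more slowly to a large dose, and reports a hypothesis of storage in tissue with slow release. Section 6 fixes the study dose: "Each participant will be provided with 250,000 IU Vitamin D3 (5 capsules) regardless of age, sex or 25OHD level".

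Section 9 makes serum calcium at one week the primary safety endpoint. It takes the efficacy proportion, 25OHD above 30 ng/mL, at the end of the study. Section 2 words the matching secondary objective as the efficacy of a single dose. Section 4 measures 25OHD after dosing at weeks 12, 26 and 52, keeps participants on their usual CF vitamins throughout, and moves anyone found below 30 ng/mL to step-wise guideline treatment.

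**The concern.** The Abstract's 14-21 days is less than half of the protocol's own figure for a high dose, and it meets even the low-dose range only at 20-21 days. The sentence that relies on it is the only pharmacokinetic support for the timing of the primary safety endpoint. 25OHD is not measured at week 1, so the trial's data cannot show where that draw falls on the curve.

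The half-life also bears on how the efficacy result can be read. If almost none of the increment is left at week 52, the end-of-study proportion reflects daily vitamins and later treatment more than the dose under test. A participant who was below 30 ng/mL at week 12 and was then treated successfully would count as a success. One who was corrected at week 12 and later drifted down, as a finite half-life predicts, would count as a failure. The plan does not give the net direction.

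**Working it through.** **Inputs.** Half-lives h: 14-21 days (Section 1), 20-30 days and 50 days (Section 3). Sampling times t: day 7, and weeks 12, 26 and 52, that is days 84, 182 and 364 (Section 4 and its study calendar). Calendar windows: week 1 ± 3 days (days 4-10); week 12 ± 30 days (days 54-114); week 52 ± 30 days (from day 334).

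**The plan's own claim.** The Abstract gives no percentage. I read the middle as about 50% of the increment produced by the dose, and follow its reasoning from half-life to level.

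**Simple decline from dosing.** Fraction left = 0.5^(t/h).

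| h (days) | day 7 | day 84 | half-lives elapsed at day 84 |
|---|---|---|---|
| 14 | 70.7% | 1.6% | 6.0 |
| 21 | 79.4% | 6.3% | 4.0 |
| 30 | 85.1% | 14.4% | 2.8 |
| 50 | 90.8% | 31.2% | 1.7 |

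For example, 0.5^(84/21) = 0.5^4 = 6.25%, and 0.5^(84/50) = 0.5^1.68 = 31.2%.

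The Abstract's claim is not reproduced. Since 84 = 12 × 7, the day-84 fraction is the day-7 fraction to the 12th power. Under this model no single half-life puts both days even within 25-75%. A level of 50% needs h = 7 days at day 7 and h = 84 days at day 84. The windows do not help: at 50 days, the earliest week-12 draw (day 54) is at 47.3%, but week 1 is at 87.1-94.6%.

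**Sensitivity to a slow rise.** Let the level rise with formation half-life a and fall with half-life h. With ka = ln2/a and ke = ln2/h, the level is [ka/(ka − ke)] × (e^(−ke·t) − e^(−ka·t)), expressed as a fraction of its peak. The documents give no value for a, so these are assumptions.

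| h | a | peak day | day 7 | day 84 |
|---|---|---|---|---|
| 50 | 7 | 23 | 65% | 50% |
| 50 | 10 | 29 | 55% | 58% |
| 50 | 13 | 34 | 48% | 65% |
| 21 | 7 | 17 | 76% | 16% |
| 21 | 13 | 24 | 60% | 29% |
| 14 | 7 | 14 | 83% | 6% |
| 14 | 13 | 20 | 68% | 16% |

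At 50 days a slow rise can put both draws near mid-range. At 14-21 days it leaves day 84 at 29% or less for a up to 13 days. At h = 21, a must reach about 20 days, close to the elimination half-life, before day 84 comes to about 45%.

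**Late 25OHD levels, on the longest half-life in the protocol (50 days).**
- Week 26: 0.5^(182/50) = 0.5^3.64 = 8.0%.
- Week 52: 0.5^(364/50) = 0.5^7.28 = 0.64%. At the early edge of the window, 0.5^(334/50) = 1.0%.
- Week 52 with a slow rise: the peak equals 0.5^(tmax/50). For a = 7, ka/(ka − ke) = 1.163 and the peak is 0.5^(23.1/50) = 0.726, so 0.643% × 1.163 / 0.726 = 1.0% of peak. For a = 13, 0.643% × 1.351 / 0.622 = 1.4%.

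**The case against.** The strongest reply is that the calculation starts the decline at dosing, while Section 3 says that the response to a large dose is much slower. That stands. A reader might infer that neither half-life can place both draws mid-range, or that week 1 is close to the peak. The documents support neither: they give no time to peak, and with 50 days and an assumed formation half-life of 7-13 days both draws are near the middle. This does not rescue the stated rationale, which uses 2-3 weeks and gives no rise rate.

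It is also fair that the middle of the range is undefined, and that the half-life is quoted for cholecalciferol while the range is for 25OHD. If the range meant is the 30-100 ng/mL target in Section 1, no half-life alone can locate a sample in it.

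A reader might further infer that scheduled calcium sampling ends at week 12 because of the half-life. The protocol does not say so. It aligns visits with three-monthly clinics, records endocrinologists' approval of the safety measures, repeats elevated values until normal, and follows related adverse events for 12 months.

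Finally, no sample size or decision rule uses the half-life, and Section 11 shows a real interest in levels sustained up to 12 months. Both are true. A sustained level under continuing vitamins and added treatment is a legitimate thing to describe, but it is not the single-dose efficacy that Section 2 sets out to determine.

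**Conclusion.** The conflict between 2-3 weeks and 50 days is plain on the text and needs no model. On the figure that the Abstract relies on, and under simple decline, the second draw comes 4-6 half-lives after dosing with 2-6% of the increment left, so the mid-range claim fails on its own premise. At 50 days it is unproven rather than refuted. None of this shows that the draws are badly timed, only that the reason given does not support them.

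The point that affects a reported result is the efficacy time point. At week 52 about 0.6% of the increment remains at 50 days, or roughly 1% of peak with a slow rise, and less at any shorter half-life under simple decline. With daily vitamins continuing and step-wise treatment given to those found low, the end-of-study proportion cannot be credited to the dose. Week 12 is the first 25OHD taken after dosing, so no earlier study level can have triggered step-wise treatment.

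Limits: first-order kinetics are assumed; the 50 days was reported at 100,000 IU and is extrapolated to 250,000 IU; if the half-life really were 2-3 weeks, little of the increment would remain even at week 12; and with one arm and continuing daily vitamins, week 12 is a better time point but not a controlled comparison.

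**What to change.** - **Sections 1 and 3:** reconcile the half-lives, saying which applies to the study dose and on what basis. Either support the mid-range rationale, with the range defined and a rise rate given, or delete it. Do not replace it with a statement that week 1 is near the peak.
- **Section 9, safety:** limit the laboratory safety conclusion to the sampled times, week 1 and week 12.
- **Section 9, efficacy:** name week-12 25OHD as the time point for single-dose efficacy. Report weeks 26 and 52 with confidence intervals as descriptive of maintenance under usual vitamins and any step-wise treatment.

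The cost is wording; week-12 25OHD is already collected and no visit or test is added. It does change a secondary endpoint's time point, so it should be recorded as an amendment, or labelled post hoc if the levels have been seen. The 12-month result would no longer be the headline efficacy figure, and any residual percentage quoted should carry the caveat that 50 days comes from a smaller dose.

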Vitamin D toxicity or hypervitaminosis D is characterized by elevated serum calcium levels or hypercalcemia (14). Due to the hypercalcemia, acute symptoms of toxicity can include muscle weakness, confusion, vomiting, anorexia, polyuria and polydipsia. In addition, hypercalcemia can be chronic, and those symptoms of intoxication from hypervitaminosis D could include bone demineralization, pain, and nephrocalcinosis.

Therefore, we believe STOSS therapy will efficaciously, safely and feasibly increase vitamin D levels to above 30 ng/mL in our pediatric CF population. We hypothesize that STOSS therapy

Date: December 20, 2016

Principal Investigator: [name]

Application Number: IRB00081746 (IND # 128487 – IND Sponsor: [name])

administered once in clinic as witnessed by a designated clinician, will maintain 25OHD levels greater than or equal to 30 ng/mL without instances of hypercalcemia (7).

4. Study Procedures

The study is a phase 2 single arm study that will assess the safety, feasibility and efficacy of a high dose of vitamin D3 as cholecalciferol in Cystic Fibrosis pediatric patients with a 25OHD level <30 ng/mL. The members of the study team will enroll 30 participants who have consented and meet eligibility criteria, including a baseline 25OHD level <30 ng/mL which is measured annually, at a minimum, as a part of the current standard of care. All patients with CF, will be consented to participate upon having his/her annual lab work collected.

As patients present with a 25OHD level < 30 ng/mL they will be screened to see if they meet full eligibility criteria for enrollment. This will include a phosphorus level and spot urine calcium to creatinine ratio which will be collected at their CF visit (patients seen at the St. Petersburg office) or within 2 weeks prior to their visit if in Sarasota or Tampa. (See section 5 for complete inclusion/exclusion criteria). Screening will also consist of a urine pregnancy test to be completed the day of the administration of the high dose of vitamin D.

After a patient meets full eligibility criteria, they will be enrolled in the study and we will administer the 250,000 IU vitamin D3 at that visit. Upon administration, each participant will be provided with an oral, one-time dosage of vitamin D3 (cholecalciferol) in the form of capsules that will be swallowed; the capsule cannot be crushed or dissolved in anything in order to be administered.

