There will not be a placebo group, as the study design does not support this; providing a placebo is not ethical in this population for this condition.

If a patient does not complete the study for any reason, meaning they do not get each set of lab work completed, their results up to that point in time will still be used in the study but their duration of participation will be noted in the results section. Every effort will be made to contact patients who are lost to follow up to ascertain the reason for withdrawal.

Date: December 20, 2016

Principal Investigator: [name]

Application Number: IRB00081746 (IND # 128487 – IND Sponsor: [name])

| Study Procedures | Study Time-points | | | | | | | |
|---|---------------------------|---------------|---------------------|---|------------------------------|--|---------------------------|------------------------|
| | Screening/ Eligibility | Base- line | Week 1 +/- 3 day | Week 1 B.*** Week 1+/- 14 days | Week 12 +/- 30 days | Week 12 B.*** Week 12 +/- 42 days | Week 26 +/- 30 days | Week 52 +/- 30 days |
| Informed Consent | X | | | | | | | |
| 25OHD Lab | X | | | | X | | X | X |
| Screening / Eligibility Verification (including pregnancy test) | X | | | | | | | |
| Eligibility screening: Spot Urine Calcium to Creatinine Ratio | X | | | | | | | |
| Study Registration | | X | | | | | | |
| Medication Review* | | X | | | X | | X | X |
| STOSS Vitamin D3 Administration | | X | | | | | | |
| Serum Calcium Test & Hypercalcemia Monitoring | | | X | X | X | X | | |
| Serum Phosphorus | X | | X | X | X | X | | |
| Parathyroid Hormone (PTH) Level (2 nd tier only) | | | | X | | X | | |
| Spot Urine Calcium to Creatinine Ratio (2 nd tier only) | | | | X | | X | | |
| Administration of Appendix A Questionnaire | | | X | | | | | |
| Adverse Event Assessment** | | X | X | X | X | X | X | X |

* Medication review will consist of surveying the patient's current daily maintenance dosage for vitamin D as previously prescribed.

** AEs and SAEs are defined per 21CFR312.32. All adverse events will be monitored and processed from study start until 30 days after study product administration. All adverse events deemed related to known vitamin D supplementation risks and/or study procedures will be monitored for 12 months post drug administration.

Date: December 20, 2016

Principal Investigator: [name]

Application Number: IRB00081746 (IND # 128487 – IND Sponsor: [name])

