We will additionally budget the cost of three participants requiring this test as a measure of safety, as this will be 10% of our overall goal number of study participants. Once we have 10% of our study participants with hypercalcemia and requiring additional safety testing, the study will be held until the DSMB can review.. The cost of three participants requiring this test at week 1 and at month 3, will cost \$441.12 (\$73.52 per test).

The cost for the urine pregnancy tests will be about \$1.98 per test or \$49.63 per box of 25 tests. We do not expect to need more than 25 pregnancy tests since these will only be used for female participants greater than 8 years old.

25OHD level is a part of the standard of care for pediatric patients with Cystic Fibrosis and will be measured for “baseline” measures prior to enrollment in the study and upon annual exam. Therefore, the cost fits within the usual cost to the participant even if they weren’t participating in the study. In addition, each time they are required to have it re-measured at 3 mo, 6 mo & 12 mo it will continue to be a part of the standard of care for assessing their vitamin D. There will be standard costs associated with it that the participant would be paying even if they weren’t participating in this study.

Vitamins/Supplements:

Vitamin D3 water miscible form will be purchased via grant funds from BioTechPharmaceutical.com for \$18.00 per 100 capsules of a water soluble and vegetarian vitamin D3 – 50,000 IU per capsule (18 cents per capsule or maximum cost per STOSS dosage of 250,000 IU is \$0.90).

CF specific vitamins are currently prescribed to all patients upon diagnosis. Therefore, participants will already be prescribed these as a part of the standard of care for the nutritional management of pediatric patients with CF and pancreatic insufficiency. Patients who are pancreatic sufficient will be on a standard regular multivitamin with minerals as a part of the standard of care. Neither of these will accrue additional cost to our center or to the patient.

Other: Support Personnel

A research coordinator will act as a part of the research time. He/she will assist in approaching eligible patients to obtain consent for participation in this study, scheduling necessary lab work, conducting the 10-item questionnaire and inputting the necessary data into the Red Cap database

Date: December 20, 2016

Principal Investigator: [name]

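### The only pre-dose 25OHD is the undated value that selected the participant, so regression to the mean and vitamin D started before dosing count as efficacy

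*Combined protocol and SAP*

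**What the plan says.** - **Source of the baseline.** Section 4 (Study Procedures) takes the qualifying level from routine care: "a baseline 25OHD level <30 ng/mL which is measured annually, at a minimum". Section 12 (Costs) gives the name baseline to this same routine value, describing it as "measures prior to enrollment in the study and upon annual exam".
- **No time limit.** Inclusion criterion b in Section 5 reads in full "Serum/blood 25OHD level < 30 ng/mL". By contrast, the calcium exclusion is dated ("Any history of hypercalcemia above upper limits of normal for age within the last six months"), and the creatinine exclusion also looks back six months.
- **Other screening labs are fresh.** Section 4 lists what is collected for eligibility: "This will include a phosphorus level and spot urine calcium to creatinine ratio which will be collected at their CF visit", "or within 2 weeks prior to their visit if in Sarasota or Tampa". 25OHD is not in that list.
- **Nothing at dosing.** The calendar row is "25OHD Lab | X | | | | X | | X | X": Screening, then weeks 12, 26 and 52. The Baseline column, where the dose is given, is blank.
- **How efficacy is judged.** Section 1 (Abstract) regards the dose as effective if levels during the study lie in 30-100 ng/mL. Section 9 (Statistical Analysis) reports the proportion above 30 ng/mL at the end of the study with a 95% confidence interval. There is no comparator, no adjustment and no change from baseline.

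**The concern.** By construction every participant stands below 30 ng/mL at the recorded baseline, so reading the later proportion as the effect of the dose amounts to assuming that none would have reached 30 without it. That assumption fails in two ways.

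First, a single reading below a cut-off is on average lower than the person's usual level. On re-measurement some of those selected will be at or above 30 whatever is given, and this happens whenever the correlation between readings is below 1, even over a short gap.

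Second, Section 3 (Background) describes the centre's current response to a low level: daily cholecalciferol for 12 weeks, then a new draw. Nothing in Section 5 excludes a child who began this after the qualifying lab. The study records the prescribed vitamin D, but the analysis makes no use of it.

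At stake is the meaning of the efficacy proportion, which is a stated secondary objective. A pre-dose value not obtained before treatment cannot be recovered afterwards.

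**Working it through.** The plan gives no efficacy figure to reproduce. The sample size of 30 is stated without a calculation. The question is what share of selected participants would re-measure at or above 30 with **no** dose effect.

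**Inputs from Section 3.** The centre reports 40% at 30-40 ng/mL, 33% below 30, and the remaining 27% printed as below 20. These categories do not fit together clearly, so two readings are used:
- Reading A: 27% below 20 and 33% at 20-30, hence 60% below 30.
- Reading B: 33% below 30, 40% at 30-40, and the remaining 27% above 40.

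**Assumptions not in the documents.** Levels are normally distributed, and the test-retest correlation r is 0.6 to 0.9.

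**Step 1: fit mean and SD.** With two cut-points x1, x2 and cumulative shares p1, p2: SD = (x2 - x1)/(z(p2) - z(p1)); mean = x1 - SD × z(p1).
- A: SD = 10/(0.253 + 0.613) = 11.5; mean = 20 + 11.5 × 0.613 = 27.1.
- B: SD = 10/(0.613 + 0.440) = 9.5; mean = 30 + 9.5 × 0.440 = 34.2.

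The fit for A is approximate: it puts about 13% above 40 ((40 - 27.1)/11.5 = 1.12), a group that Reading A does not contain.

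**Step 2: probability of re-measuring at or above 30.** P = 1 - P(both readings < 30)/P(first < 30), from the bivariate normal.

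| r | A: both < 30 | A: P | A: of 30 | B: both < 30 | B: P | B: of 30 |
|---|---|---|---|---|---|---|
| 0.9 | 0.530 | 0.116 | 3.5 | 0.265 | 0.197 | 5.9 |
| 0.8 | 0.501 | 0.165 | 5.0 | 0.237 | 0.281 | 8.4 |
| 0.7 | 0.478 | 0.204 | 6.1 | 0.216 | 0.346 | 10.4 |
| 0.6 | 0.457 | 0.238 | 7.1 | 0.197 | 0.403 | 12.1 |

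For example, A at r = 0.9: 1 - 0.530/0.600 = 0.116. The range is 12-24% under A and 20-40% under B. Vitamin D started before dosing would add to this; the documents give no figure for it.

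**Step 3: would restricting to those still below 30 at dosing cure it?** Only in part. With three equally correlated readings, the share reaching 30 on the third, given that the first two were below 30, is 7-17% under A and 11-28% under B (r from 0.9 down to 0.6). The subset also shrinks to 30 × (1 - P): about 26.5 down to 22.9 participants under A, and 24.1 down to 17.9 under B. Precision is already low at 30: 15/30 has an exact 95% interval of 31-69%, and 24/30 one of 61-92%.

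**The case against.** The strongest reply is that little of the plan rests on this. Efficacy is secondary, the study is openly unpowered, and the primary endpoint, serum calcium at one week, does not involve the baseline 25OHD. That is right, and it sets the weight of the point.

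A reader might also infer more than the documents support:

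- **That a before-after gain is inflated.** Section 9 plans no change from baseline. The bias enters only through the proportion attaining 30.
- **That the qualifying value may be as much as a year old.** Section 4 places consent at the annual lab collection, and clinic visits are usually about three months apart. The gap is probably around one clinic interval. The defect is that no limit is written.
- **That season drives the result.** The end-of-study draw at week 52 ± 30 days falls in about the same season as dosing. Season matters mainly at weeks 12 and 26, for which Section 9 names no proportion.
- **That some participants are known to be at or above 30 when dosed.** That is an expectation from a model, not an observation.
- **That the future trial's sample size would necessarily be wrong.** If that trial used the same entry rule, its treated arm would carry the same selection. What would be missing is a control rate, and a dosing-day assay does not supply one.

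Interim vitamin D is partly covered, since prescribed intake including total IU is recorded at each study visit. Recording it does not bring it into the analysis. Nor does a short gap remove regression to the mean. The core of the point therefore stands.

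**Conclusion.** The point holds as a cheap improvement to a secondary endpoint. The value used to select participants has no maximum age and is the only pre-dose value, and the plan credits the dose with any later level of 30-100 ng/mL. With no dose effect, about 12-24% of participants (roughly 3 to 7 of 30) would re-measure at or above 30 if 60% of the clinic is below 30, or 20-40% (roughly 6 to 12 of 30) if 33% is. These figures rest on normality, on an assumed correlation of 0.6-0.9, and on two readings of ambiguous centre percentages. The direction needs only imperfect correlation between readings.

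**What to change.** 1. Keep the eligibility threshold, and state a maximum interval from the qualifying 25OHD to dosing.
2. Add a 25OHD assay to the phosphorus sample already drawn at the visit or in the two weeks before it, and mark it in the calendar. Eligibility stays on the qualifying value, so dosing need not wait for the result.
3. Use this value as the analysis baseline. Report how many participants were already at or above 30 before dosing, and show the week 12, 26 and 52 proportions beside that pre-dose proportion, each with its 95% interval.
4. Give the result among those still below 30 only as supplementary, because it selects again on a low value and reduces n.
5. State that week-52 levels are not attributable to the dose alone. Section 4 places anyone found below 30 after dosing on step-wise vitamin D, and a pre-dose assay does nothing about that.

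The cost is about 30 assays billed to research, with no extra needle or visit, and possibly a less favourable efficacy statement.
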